In Phase 1 (R21), the study team worked with the CFD to train Emergency Medical Service (EMS) teams to obtain authorization for release of contact information from individuals after an overdose reversal. The experimental pilot study tested the feasibility of each step in the intervention protocol and compared individuals who were randomly assigned to receive either a treatment referral pamphlet or the RIMO intervention on treatment received at 30-day follow-up. Qualitative data was also obtained from a focus group with participants in the RIMO group. A total of 75 individuals who had received naloxone from EMS were informed about the study; 50 (67%) of these signed the authorization form and provided their contact information; 33 met with the study team, consented to participate, and were randomized. Compared to the control group, the RIMO group (n=16) had higher odds of receiving any treatment for opioid use (OD = 7.94) and any MAT (OR = 20.2); they received significantly more days of opioid treatment (15.2 vs. 3.4) and more days of MAT (11.2 vs. 0.76) relative to the control group (n=17; all p < .05). Qualitative data highlighted the core components of the RIMO intervention. The pilot study demonstrates the feasibility of partnering with EMS and using the RIMO intervention to address the challenges of linking and engaging individuals into MAT after opioid overdose. These findings have been submitted for publication ([name] et al., under review) and were used to refine the study design for phase 2.

In Phase 2 (R33), research staff will continue to work with the CFD's EMS division and CPD to identify people who have just had an opioid overdose reversed with naloxone, recruit them into the trial, randomize them to a passive referral (via a brochure) vs. the RIMO experimental group. Using the study recruitment and RIMO procedures refined in Phase 1, a total of 350 individuals will be recruited and randomly assigned to the "referral to MAT" control or to "RIMO". All participants will receive standardized assessments at baseline and 3, 6, and 9 months post-randomization. The study's aims and their associated hypotheses are:

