## **2. Primary and secondary objectives and outcome measures**

The primary outcome measure for the study is the GAIN-Quick Version 3 (GAIN-Q3). The GAIN-Q3 includes 4-6 symptom count screeners that are correlated .9 or more with the 11 to 43-symptom version in the full GAIN. It also has cut points with excellent (~90%) sensitivity, specificity, and area under the curve (AUC) relative to the full GAIN in 9 problem areas related to substance use disorders, physical health, internalizing and externalizing mental health disorders, as well as school, work, stress, HIV risk behaviors/victimization, and crime/violence. The days of use measures have been validated against the Timeline Follow-back, collateral reports, and urine and saliva tests. The GAIN-Q3 also includes summary measures for health care utilization, functional impairment, quality of life, and life satisfaction. The GAIN-Q3 includes the behavioral health screener and health care utilization measures that have been recommended by NIH's Phenx common data elements as two of the most reliable, valid, efficient, and inexpensive tools in the field. At each follow-up, the Q3 follow-up will be supplemented with a) a section on overdose and naloxone experiences, and b)

symptom counts from the OUD scale. Table 2.1 crosswalks the key independent measures and secondary outcomes from the hypotheses to their definitions, reliability, data sources, and the specific aims they address.

Table 2.1. Crosswalk of Variables, Definition, and Aims	H1	H2	H3
Experimental Assignment: Based on computer-generated urn randomization, participants will be assigned to the referral only control group or the experimental RIMO condition.	R	R	R
MAT Time to Initiation: Days from index naloxone administration to the initiation of any kind of MAT, from treatment records.	O		
Length of Staying on Medication: Days between MAT initiation and discharge, from treatment records.	O		
MAT Days: Total days of MAT over 9 months from GAIN-Q3 and treatment records.	O	M	M
Time to Relapse: Days from randomization to next subsequent use of opioids or heroin based on GAIN Q3 follow-up interviews and urine tests.		O	
Opioid Days of Use: Days of opioids and/or heroin use summed over the GAIN-Q3 follow-up interviews.		O	M
Opioid Overdose: Number of opioid-related overdose[s] summed over the GAIN-Q3 follow-up interviews.		O	

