Opioid Related Fatality: Any ICD-10 cause of death related to opioid overdose (T40.1, T40.2, T40.3, T40.4, T40.6, X42, X44, X62, X64, Y12, Y14) in CDC death records.		O	
Opioid Use Disorder: The average of 11 past 90-day items on the Opioid Use Disorder Scale (11 DSM-5 symptoms) self-reported from the GAIN-Q3 follow-up interviews			O
Physical Health: The average of 5 past 90-day items on the Health Problem Screener (worried about health, pain, health kept participant from meeting responsibilities) from GAIN-Q3 follow-up interviews.			O
Mental Health: The average of the past 90-day items across the Internalizing (symptoms of depression, anxiety, trauma, suicide) or Externalizing (symptoms of attention deficit, hyperactivity, conduct, gambling) Disorder			O
Cost of Health Care Utilization: Sum of the quarterly costs of health care from the GAIN-Q3 follow-up interviews; based on the frequency of health, mental health or substance-related ED visits, hospitalizations, residential treatment, outpatient surgery, MAT, intensive outpatient, outpatient treatment days/times multiplied by their respective costs using published estimates by health economists, adjusted for inflation using the CPI.			O
Key: R=Randomization, O=Outcome, M=Mediator			

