## **10. Statistical analysis plan**

Missing data. Participants will complete their baseline interview prior to randomization. Based on prior studies conducted by the applicants, it is expected that approximately 90% or more of the 3, 6, and 9-month post-randomization interviews will be completed. Among these completed interviews, prior studies conducted by the team indicate that less than 1% will have additional missing data on any of the core items required to test the study hypotheses. Multiple imputations will be used to replace the small amounts of missing data to allow the least biased estimate for each analysis. To further reduce potential bias, analyses will be rechecked by running them without missing data. If there are any clinically significant differences ( $d > |.2|$ ), a general latent variable framework will be used to analyze non-ignorable or systematic missing data that tests whether missing data is qualitatively different by condition.

Survival Analysis for Time to MAT Initiation and Time on Medication (Aim 1). The primary outcome is the days from randomization until the initiation of any kind of MAT. Relative to the referral only control group, the direct effects of RIMO on reducing the days from randomization to initiation of any MAT (H1a) and increasing the days on medication after initiation (H1b) will be evaluated with a Cox Regression model using IBM SPSS version 24 with random assignment to RIMO as the main predictor, as the investigators have done in earlier experiments. It will be examined after the point of randomization and after each follow-up interview. Survival analysis incorporates information about censorship (e.g., death, people who were not admitted to MAT within 9 months) and can incorporate covariates if needed. The output includes a case summary (e.g., missing data, other problems, descriptive statistics) and an evaluation of each term (e.g., beta, its standard error, Wald, its probability, the odds ratio, the 95% confidence interval for the odds ratio). The beta can also be converted to a Cohen's effect size *d*. All analyses will use an intent-to-treat approach (i.e., participants are analyzed as assigned regardless of their actual level of participation in RIMO). We will also conduct a secondary analysis of the time to MAT initiation after each RIMO checkup to understand the pattern over time as we have done with earlier experiments.

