Direct Effects of RIMO on MAT (Aim 1). Relative to the referral only control group, the direct effects of RIMO on reducing dropout and receiving more total days of MAT will be evaluated using a multilevel structural equation modeling (MSEM) with mixed effects in MPlus (version 7.4). The analysis will model observations (Level 1) nested within participants (Level 2), with participants modeled as a random factor anchored on the baseline version of the dependent variable. Randomization to RIMO will be modeled as a Level 1 predictor. We will check for the need to use models that adjust for counts or zero saturation.

Direct Effects of RIMO on Secondary Outcomes of Time to Relapse, Opioid Use and Overdose (Aim 2) and Death, OUD, Health, Mental Health, and Health Care Utilization (Aim 3). Relative to the referral only control group, the direct effects of RIMO on time to first relapse (H2) will be evaluated with a survival analysis similar to Aim 1 H1. It will be examined after the point of randomization and after each follow-up interview. The direct effects of RIMO on days of opioid use (H2), opioid overdoses (H2), opioid-related fatality (H3), symptoms of OUD (H3), physical health problems (H3), mental health symptoms (H3), and the cost of health care utilization (H3) will also be evaluated using a series of MSEM with mixed effects in MPlus modeled in the same way as above. Most of the above variables are relatively continuous, but we will check for the need to use models that adjust for counts or zero saturation. For opioid-related fatality (H3), we will define the dependent variable as dichotomous in MPlus (equivalent to using logistic regression).

Indirect Effects of RIMO (Aims 2 and 3). To evaluate indirect effects, we will determine the extent to which the direct effects of RIMO on the above dependent variables are changed by of days of MAT received (H2 & H3) and/or days of opioid use (H3) using the Preacher and colleagues framework for testing mediation in MSEM with REML in MPlus. Loss of statistical significance in the path coefficient from the intervention conditions to the other outcome variables would indicate full mediation; a reduction in the path coefficient would indicate partial mediation. Change will be evaluated using MacKinnon's joint-significance testing of the path *z*-scores with a Sobel test using a standard error based on bootstrapping and criteria of  $p < .05$  on the degree of change.

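### Time to relapse (H2a): as the plan reads, a fatal opioid overdose with no earlier recorded use is censored instead of counted as relapse

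*Combined protocol and SAP*

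**What the plan says.** Table 2.1 (Section 2) defines time to relapse as "Days from randomization to next subsequent use of opioids or heroin based on GAIN Q3 follow-up interviews and urine tests". No other source is named. The post-randomization assessments come at three fixed points: "All participants will receive standardized assessments at baseline and 3, 6, and 9 months post-randomization".

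Section 10 gives the method in the paragraph on secondary outcomes: "time to first relapse (H2) will be evaluated with a survival analysis similar to Aim 1 H1". The Aim 1 analysis it points to "will be evaluated with a Cox Regression model using IBM SPSS version 24 with random assignment to RIMO as the main predictor", and the same paragraph says: "Survival analysis incorporates information about censorship (e.g., death, people who were not admitted to MAT within 9 months".

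Opioid-related death is collected separately. Table 2.1 defines it as "Any ICD-10 cause of death related to opioid overdose", taken from CDC death records, and Section 10 analyses it on its own: "For opioid-related fatality (H3), we will define the dependent variable as dichotomous in MPlus (equivalent to using logistic regression". The plan nowhere makes a fatal opioid overdose a relapse event, uses a composite or competing-risk version of H2a, or gives H2a its own rule for death.

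**The concern.** Relapse is defined as the next opioid use after randomization. A fatal opioid overdose meets that definition, but the sources and the censoring rule together leave no route by which it can be recorded as relapse. Someone who dies before the first follow-up has no post-randomization interview or urine test at all. Someone who dies later, after assessments that showed no use, is in the same position.

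The population makes this realistic: every participant has had a naloxone-reversed overdose within the past week (Section 3). The sponsor's own hypothesis H3a is that RIMO affects opioid-related fatalities, so the number of uncounted relapses could differ by arm. Censoring then depends on the outcome itself, which breaks the independent-censoring assumption of the Cox model. At stake are the H2a hazard ratio and its event count.

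**Working it through.** **Textual check.** Four statements decide the coding of a participant who dies of an opioid overdose with no earlier recorded use.

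1. Event sources: interviews and urine only (Table 2.1). There is none, so no relapse event.
2. Method: modelled on the Aim 1 survival analysis (Section 10).
3. Death in that analysis: an example of censoring (Section 10). The participant is censored.
4. Opioid death: a separate dichotomous outcome under H3 (Section 10). It does not enter H2a.

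Each such death removes one relapse event.

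**Inputs for size.** From Section 4: 350 participants, 175 per arm. The documents give no death rate, relapse rate or hazard ratio for H2a, so there is no figure of the plan's own to reproduce. Everything else here is assumed: opioid mortality over 9 months of 3-10% (control) and 2-4% (RIMO), spread evenly over 270 days; control relapse of 70-90% by day 270 with exponential times; a true hazard ratio (HR) of 0.79; assessments at days 90, 180 and 270.

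**Events lost.** A death in days 0-90 is always unrecorded. One in days 90-180 is unrecorded if there was no relapse by day 90, and one in days 180-270 if there was none by day 180. With S(t) the probability of no relapse by day t, the chance that an opioid death hides a relapse is q = [1 + S(90) + S(180)] / 3.

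- 90% relapse: control S(90) = 0.1^(1/3) = 0.464 and S(180) = 0.215, so q = 0.560. RIMO, raising each to the power 0.79: 0.545 and 0.297, so q = 0.614.
- 70% relapse: control 0.669 and 0.448, so q = 0.706. RIMO 0.728 and 0.530, so q = 0.753.
- Low end (3% v 2%, 90% relapse): 175 × (0.03 × 0.560 + 0.02 × 0.614) = 5.1.
- High end (10% v 4%, 70% relapse): 175 × (0.10 × 0.706 + 0.04 × 0.753) = 17.6.

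So about 5 to 18 events are lost.

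**Effect on the hazard ratio.** Large-sample simulation under the same assumptions, with Cox fits. Change = (censored − counted) / censored; a positive value means the planned analysis is nearer 1.

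| Opioid deaths, control v RIMO | Control relapse | HR, death censored | HR, opioid death counted | Change |
|---|---|---|---|---|
| 3% v 2% | 90% | 0.791 | 0.788 | 0.4% |
| 3% v 2% | 70% | 0.792 | 0.787 | 0.6% |
| 10% v 4% | 70% | 0.802 | 0.759 | 5.4% |
| 3% v 4% | 90% | 0.787 | 0.795 | −1.0% |
| 3% v 4% | 70% | 0.786 | 0.801 | −1.9% |

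**Second set-up.** Trial-sized simulation (175 per arm, 150 replicates, assumed HR 0.8, control relapse 60%), with all the fatal overdoses in days 1-90. Mean HR with death censored v counted, by number of deaths in control/RIMO:

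- 2/2: 0.80 v 0.80
- 5/2: 0.81 v 0.79
- 10/4: 0.80 v 0.77
- 4/10: 0.78 v 0.85

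The direction follows the arm with more deaths, and the shift vanishes when deaths are few and balanced.

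**Against sampling error.** At HR 0.79, RIMO relapse is 1 − 0.3^0.79 = 61% or 1 − 0.1^0.79 = 84%. Expected events are 175 × (0.70 + 0.61) = 229 to 175 × (0.90 + 0.84) = 305. With SE(log HR) ≈ √(4/events), that is 0.13 to 0.11. The largest shift in the table is ln(0.802/0.759) = 0.055, about half a standard error or less.

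**The case against.** The strongest reply is that the rule is inherited, not stated. The censoring sentence belongs to Aim 1, its list is only of examples, and its other example (not being admitted to MAT) cannot apply to relapse. That is correct, and the point is worded accordingly. Still, it is the only rule for death that the plan offers H2a, and nothing contradicts it. The multiple imputation in Section 10 is for missing data and is not said to cover deaths.

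Second, Section 8 expects almost everyone to be using opioids when first contacted. If use resumes quickly, most people who die after month 3 will already have a recorded relapse. This stands and narrows the problem mainly to deaths before the first follow-up. With deaths spread evenly, that is one third of them: 175 × (0.03 + 0.02) / 3 = 2.9 to 175 × (0.10 + 0.04) / 3 = 8.2, or about 3 to 8 participants under the same rates.

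Third, H2a is secondary, and opioid fatality is compared by arm under H3a. A reader might infer that excess deaths under RIMO would be concealed. The documents do not support that, because the fatality comparison would show them. It does not repair the H2a hazard ratio, however.

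A reader might also infer that deaths from other causes credit the time since the last interview as relapse-free. The plan gives no date at which a death is censored, so that does not follow from the text.

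**Conclusion.** The point holds as a gap in the H2a event definition. Following the plan as written, a fatal opioid overdose with no earlier recorded use is coded as a non-event although it satisfies the plan's own definition of relapse.

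The effect is small and falls on a secondary outcome: under the assumed rates, about 5 to 18 lost events and hazard ratio shifts of roughly 0.4-5% toward 1 when control deaths are higher. The 5% figure needs 10% opioid mortality in control, which nothing in the documents supports or excludes. A larger shift (0.78 v 0.85) needs a marked excess of early RIMO deaths.

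It is tempting to call the bias one of known direction. It is not: at 3% v 4% it reverses by 1-2% and makes RIMO look better than it should. The change is worth making because the definition would then match its own wording at almost no cost, and because the choice is best fixed before outcomes are compared by arm.

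**What to change.** In Table 2.1 and Section 10, state that an opioid-related death, identified from the CDC death records already used for H3a, counts as an H2a relapse event, dated at death when no earlier use is recorded. Write the H2a handling of death in its own sentence so that it no longer rests on similarity to Aim 1. Keep the analysis that censors these deaths as a sensitivity analysis, and report the number of events added by arm.

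The cost is about one sentence in each place. No new data are needed: cause of death is already planned, deaths are logged during follow-up (Section 21), and dates are already converted to days from randomization (Section 9).

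One small downside should be acknowledged: the death date is the latest possible relapse date, since unrecorded use may have come before it.

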### 4. Sample size and power calculation

We plan to recruit and randomize 350 participants over 24 months. There should be 99% or more power to determine the direct effect of RIMO on the primary outcome of time to MAT initiation (H1a) assuming a sample size of 350 patients, randomized into two groups of 175 each, interviews at 4 time points for the main analysis (baseline, and 3, 6, and 9 months post-randomization), our average completion rate of 94+% per follow-up wave, and a moderate to large effect size of  $d=3.0$ . This expected effect size was based on the natural log of the odds ratio ( $\text{Log}^e(\text{OR})=d$ ) of initiating MAT ( $\text{OR}=20.2$ ) from RIMO Pilot study ([name] et al., under review). For the other tests of direct effects, the effective n for power calculations in repeated measures analysis varies between a lower bound of the number of unique people per group ( $N=175$  people), and an upper bound of the number of people randomized plus the completed follow-up interviews or 668 observations per group ( $O=(175 \text{ people at intake} + \text{average of } 94\% \times 175 \text{ people} \times 3 \text{ follow-ups})$ ) as a function of the intra-class correlation coefficient (ICC) associated with the individual and the number of repeated measures (RM) per person ( $\text{effective } n'=O/(1+\text{ICC}(\text{RM}-1))$ ). In our prior studies, ICC of the other dependent

variables ranged from .13 to .34. Thus the effective n= range from 429 to 398 per group and be capable of detecting an effect size of  $d=0.2$  or more with 80% power for a two-tailed test of  $p<.05$  of effect sizes  $d=.2$  or more. For mediation analysis, the tests should also have 80%+ power for a 2-tailed test of  $p<.05$  and an indirect effect size of  $d=.2$  or more.

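### Sections 4 and 10 disagree on whether baseline is an outcome or a covariate in the multilevel models, so the RIMO effect and its power are not pinned down

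*Combined protocol and SAP*

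**What the plan says.** Section 10 (Direct Effects of RIMO on MAT, Aim 1) describes a two-level model with observations within participants. Participants are a random factor tied to the baseline value of the outcome, and "Randomization to RIMO will be modeled as a Level 1 predictor". It names no visit effect, no post-baseline indicator and no arm-by-visit term. The next paragraph carries the model to Aims 2 and 3: those outcomes "will also be evaluated using a series of MSEM with mixed effects in MPlus modeled in the same way as above".

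Section 4 assumes "interviews at 4 time points for the main analysis (baseline, and 3, 6, and 9 months post-randomization"). For the tests of direct effects other than H1a it takes as the top of the range for effective n "an upper bound of the number of people randomized plus the completed follow-up interviews or 668 observations per group". It then deflates that count using the ICC and "the number of repeated measures (RM) per person", and concludes that d=0.2 is detectable with 80% power.

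Table 2.1 in Section 2 points another way. Opioid days and overdoses are sums over follow-up interviews, OUD symptoms and physical health come from follow-up interviews, and MAT days is a nine-month total.

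**The concern.** Section 4 needs the intake interviews as observations to reach 668. Section 10 can be read as using baseline only for adjustment. The difference matters because baseline precedes randomization, so the true arm effect there is zero. A model that treats baseline rows as outcomes must say how the arm term behaves at baseline and how change over time is handled, and Section 10 says neither.

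Shared change is plausible here. Section 3 admits people within a week of an overdose who have had no treatment for 30 days, and Section 8 expects almost all to be using. MAT days, for example, can hardly do anything but rise in both arms. At stake are the estimate, the error rate and the stated power for H1c, H1d, H2b, H2c and the H3 interview outcomes. An analyst could also choose among the codings after seeing the data.

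**Working it through.** **Inputs.** From Section 4: "randomized into two groups of 175 each"; "our average completion rate of 94+% per follow-up wave"; ICCs of other dependent "variables ranged from .13 to .34"; two-sided .05; d=0.2. Assumption: the outcome has total variance 1 and a random intercept with variance ρ = ICC. The size of any shared change is also assumed, because the documents give none.

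**The plan's own figures.**
- Observations per arm: 175 + 0.94 × 175 × 3 = 668.5, which reproduces 668.
- n per arm for d=0.2 at 80% power: 393. Power is Φ(d√(n/2) − 1.96), so the stated effective n of 398 to 429 gives 80.5% to 83.4%.
- Effective n = 668.5/(1 + ρ(RM − 1)). RM=4 gives 481 (ρ=.13) to 331 (ρ=.34). RM=3 gives 531 to 398. Only 398 of the stated pair is reproduced, and it combines a four-wave numerator with three repeats. So Section 4 is itself not consistent about baseline.

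**Reading A: baseline rows are outcomes and arm is constant within person.** With complete data the coefficient is the difference in four-visit means, 0.75d.
- 0.75 × 0.2 = 0.150. At 94% follow-up the share is about 493.5/668.5 = 73.8%, giving about 0.148.
- SE = √(2(ρ + (1 − ρ)/4)/175) = 0.063 (ρ=.13) or 0.076 (ρ=.34).
- Power = Φ(0.150/SE − 1.96) = 66% or 51%; at 94% follow-up, about 63% or 48%.
- Adding a visit main effect changes nothing. With balanced visits it is orthogonal to arm, and the coefficient stays at 0.150.

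**Reading B: baseline rows are outcomes, arm is 1 only on RIMO follow-up rows, and there is no visit term.** In random-intercept GLS the coefficient is (W_xy + φB_xy)/(W_xx + φB_xx), where W and B are within- and between-person sums and φ = (1 − ρ)/(1 + 3ρ).
- Per RIMO participant, W_xx = 0.75 and B_xx = 1.125. A change common to both arms contributes 0.75 per SD through W_xy and nothing through B_xy.
- Share absorbed = 0.75/(0.75 + 1.125φ) = 1/(1 + 1.5φ). For ρ=.13, φ=.626 and the share is 52%. For ρ=.34, φ=.327 and the share is 67%.
- SE = √((1 − ρ)/(175(0.75 + 1.125φ))) = 0.0585 or 0.0581.
- With no true effect and an assumed shared change of 0.2 SD, the coefficient is 0.103 or 0.134 and the false-positive rate is 42% or 64%. At 0.1 SD the rate is 14% to 21%; at 0.5 SD it exceeds 99%.
- Adding a post-baseline term restores 0.20 and 5%, with power of 84% or 80% (complete data).

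**Reading C: baseline is a covariate and only follow-ups are outcomes.** The arm coefficient is 0.20 and the false-positive rate about 5%, even without a visit term.
- Observations per arm: 0.94 × 175 × 3 = 493.5.
- The plan's formula with RM=3 gives 493.5/1.26 = 392 and 493.5/1.68 = 294, hence power of 80% and 68% before credit for baseline adjustment.
- With baseline adjustment, SE = √(2(ρ + (1 − ρ)/3 − ρ²)/175) = 0.068 or 0.071, so power is 84% or 80%; at 94% follow-up it is about 82% or 79%.

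**The case against.** The strongest reply is that Reading C is the natural one. Tying the model to baseline suggests covariate adjustment, and Table 2.1 defines these outcomes on follow-up data. Dropout from MAT has no sensible pre-randomization value. The four-time-point phrase in Section 4 sits in the sentence on power for H1a, a Cox analysis, and 668 is called only an upper bound. Reading B is written nowhere. It follows only from taking the Level 1 label literally, and it fits poorly with analysis as assigned. Section 10 is also a short outline, so silence on visit terms does not show that they will be left out.

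Much of this stands. A reader might infer that the plan as written must either credit RIMO with shared change or dilute its effect by a quarter. The documents do not support that, because Reading C is open and unbiased. A reader might also blame the dilution on the missing visit term; it comes from applying a constant arm term to baseline rows.

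The reply does not remove the inconsistency. Reading C cannot supply 668 observations, and Section 4 builds its effective n for these models on that count. Section 4 makes no baseline-adjustment argument that would recover the power. Nor is an arm assignment that is constant within person naturally a Level 1 variable.

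**Conclusion.** The point holds as an inconsistency between Sections 4 and 10 with real consequences, not as a demonstrated bias. Each reading requires a correction to one section or the other:
- Reading A understates the effect by about a quarter and gives power of roughly 50-66%.
- Reading B absorbs 52-67% of shared change.
- Reading C is unbiased but has about 493 observations per arm, with power of about 80% to 68% by the plan's formula, or about 79-84% once baseline adjustment is credited.

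The absorption shares, dilution and power figures rest on the plan's sample size and ICC range and on a random-intercept model for a roughly continuous outcome; the closed forms assume complete data unless stated. The false-positive rates also depend on an assumed shared change and are illustrations only. The primary Cox comparison of time to MAT initiation is not affected.

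**What to change.** In Section 10, replace the model statement with one of these:
- (a) Outcomes are the 3-, 6- and 9-month observations only, with visit as a categorical fixed effect, the baseline value as covariate, and randomized arm as a participant-level predictor.
- (b) All four visits are outcomes, with categorical visit terms and arm terms at follow-up visits only, so that the arms share a common baseline mean.

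Under either form, define the RIMO effect as the arm contrast averaged over the three follow-ups, and state that Aims 2 and 3 use the same form. Then restate the observation count, RM, effective n and power in Section 4 to match; if baseline adjustment is relied on for power, say so. Adding visit indicators without settling the arm coding would leave the dilution of Reading A in place.

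The cost is wording and a few model terms, with no new data or participants. Under form (a) the stated count falls to about 493 per arm, and under either form the stated power may end slightly below 80% at the upper ICC.
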